6. STUDY SETTING

Participants will be recruited from hospitals in Northwest England and North Wales. The data collection and intervention delivery will occur entirely remotely, so participants may complete the study from any place they have internet or telephone access.

7. ELIGIBILITY CRITERIA

Participants will be recruited from hospitals and clinics in the United Kingdom.

7.1. Inclusion Criteria

For inclusion in the study, subjects must satisfy all of the following criteria:

- Been diagnosed with cancer in the past six months
- Have received anti-cancer treatment with curative intent
- Aged 16 years or over
- Sufficiently proficient in English to provide informed consent and use the online programme
- Able to access the internet
- Currently have (or willing to set up) an active email address

7.2. Exclusion Criteria

Subjects for whom any of the following criteria apply are not eligible for inclusion in the study:

• Severe comorbidity considered by the screening nurse to interfere with the individual's ability to complete the requirements of the study or provide informed consent (e.g., intellectual disability or neurological impairment).

8. TRIAL PROCEDURES

8.1. Recruitment

8.1.1. Screening

Clinical research network (CRN) staff will review patients' clinical information to determine eligibility. CRN staff will be provided with a standardised screening log by the study team. CRN staff will complete this standardised screening log for each fortnight period from the point of the Sponsor Green Light at each site. CRN nurses completing this form are instructed to redact information in the first two columns to ensure anonymity before sharing with the study team; the unredacted version should be retained at the clinical site for the remaining information to be completed (if applicable) following consent being received.

8.1.2. Patient Identification and Approach

Where the next scheduled appointment is over 6 weeks into the future, staff will conduct patient approach over the telephone. Where eligible patients have an appointment scheduled within the next 6 weeks, Clinical Research Network staff will introduce the study either in person at a scheduled hospital appointment or via a telephone conversation. Though face-to-face discussion is preferred for patients who have an appointment scheduled within the next 6 weeks, CRN staff may use their own discretion in choosing the best approach method for each patient. Approached patients will be provided with a hard-copy information pack about the clinical trial and given the opportunity to ask questions about the study. Participants who have been approached entirely via telephone will have this information pack posted to them. For any questions which Clinical Research Network staff are unclear about, participants will be directed to contact the Trial Coordinator.

8.2. Consent

The informed consent process will consist of participants being provided with a written Participant Information Sheet containing details about the clinical trial and being provided with a verbal description of the clinical trial by Clinical Research Network staff. The participant will also have the opportunity to ask questions about the trial to members of the Clinical Research Network staff directly, and they will be provided with contact details for the research team for any further queries they would like to discuss.

Participants' information packs will contain the URL for an online survey, which they will be directed to complete if they would like to proceed with study participation. The first page of this survey will again display the Participant Information Sheet. Provided that the participant is happy to proceed with the study, they will provide informed consent to take part in the study through via an e-consent form. Based on our assessment that this study poses minimal

risk to participants, we have deemed that a simple electronic signature, consisting of a tickbox (next to which they type their initials) and a typewritten name and date of birth is a sufficient indication of informed consent, as per the Health Research Authority's joint statement on seeking consent by electronic methods (https://www.hra.nhs.uk/media/documents/hra-mhra-econsent-statement-sept-18.pdf).

Both the informed consent discussion and the Participant Information Sheet will include explanations of the following:

- That the trial involves research;
- The purpose of the trial;
- The trial treatment(s) and the probability for random assignment to each treatment;
- The trial procedures to be followed;
- The participant's responsibilities;
- Those aspects of the trial that are experimental;
- The reasonably foreseeable risks or inconveniences to the participant;
- The reasonably expected benefits of the study;
- The alternative procedure(s) or course(s) of treatment that may be available to the participant, and their important potential benefits and risks;
- The anticipated prorated payment, if any, to the participant for participating in the trial;
- The anticipated expenses, if any, to the participant for participating in the trial;
- That the patient's participation in the trial is voluntary and that the patient may refuse to
 participate or withdraw from the trial, at any time, without penalty or loss of benefits to
 which the participant is otherwise entitled;
- That the monitor(s), the auditor(s), the REC and the regulatory authority(ies) will be granted direct access to the participant's data, without violating the confidentiality of the subject, to the extent permitted by the applicable laws and regulations and that, by signing a written informed consent form, the participant or participant's legally acceptable representative is authorizing such access;
- That records identifying the participant will be kept confidential and, to the extent permitted by the applicable laws and/or regulations, will not be made publicly available.
 If the results of the trial are published, the participant's identity will remain confidential;
- That the participant or participant's legally acceptable representative will be informed in a timely manner if information becomes available that may be relevant to the participant's willingness to continue participation in the trial;
- The person(s) to contact for further information regarding the trial and the rights of trial subjects, and whom to contact in the event of trial-related injury;
- The foreseeable circumstances and/or reasons under which the patient's participation in the trial may be terminated;
- The expected duration of the patient's participation in the trial;
- The data protection requirements for the trial and open access arrangements for data sharing;
- The approximate number of participants involved in the trial.

Following completion of the informed consent form, a member of the research team will store the consent form securely and send a copy of the survey output of the e-consent form to the recruiting site for inclusion in the participant's clinical notes.

Should any participant lose capacity after previously providing informed consent to take part in the study, the participant will be withdrawn from the study, but data captured up to that point will be retained. Specific consent will be sought to collect clinical data posthumously in the event of participant death.

8.2.1. Additional consent provisions for collection and use of participants' data and biological specimens in ancillary studies

No additional consent will be sought.

8.3. Participant Numbering

Each participant number will consist of one prefix corresponding to the hospital from which they were recruited, an additional prefix corresponding to the clinical group within that hospital from which they were recruited, and an additional number corresponding to the order in which each participant was recruited within each given clinical group. For example, the first participant recruited from hospital 4, clinical group 2, will be labelled '040201', the second participant from this clinical group will be labelled '040202', etc.

8.4. Randomisation Scheme

This study is a parallel randomised controlled trial (RCT), with equal numbers of participants randomised to the intervention and control arms. Permuted block randomisation to active treatment versus waitlist control groups will be conducted on a 1:1 ratio.

8.5. Blinding

The study will be single-blind, such that the Chief Investigator, Trial Co-ordinator and team members involved with data analysis will not know the treatment to which a particular subject has been randomised. The randomisation scheme will be set up by the Liverpool Clinical Trials Centre. Two members of the research will be deliberately unblinded so that they can conduct randomisation using this system.

8.6. Unblinding

The investigator reserves the right to conduct unblinding in exceptional circumstances where a participant's health or safety is reasonably believed to be compromised by continued investigator blinding to the participant's allocated treatment arm.

8.7. Evaluations

8.7.1. Screening

CRN staff will refer to patients' clinical data to confirm that all inclusion criteria and no exclusion criteria are met. The CRN staff member will verbally clarify with the patient if any of these criteria are not included or unclear in the available clinical data.

8.7.2. Baseline Assessment

For the baseline assessment, participants will be sent a link to a survey containing the following questionnaires: demographic characteristics (including age, sex, ethnicity, employment status, education, relationship status, marital status, household income, and residence in England or Wales), the Post-Traumatic Stress Scale (Foa et al., 1993), the DASS-21 (Lovibond & Lovibond, 1996), the QLQ-C30 (Aaronson et al., 1993), the PIC (Hulbert-Williams et al., 2019), the UK Cancer Costs Questionnaire, the MOS Social Support Survey (Sherbourne & Stewart, 1991), the Difficulties in Emotion Regulation Scale (Gratz & Roemer, 2003), the Miller Behavioural Style Scale – Short Form (Miller, 1987; Steptoe, 1989), and the CompACT (Francis et al., 2016).

8.7.3. Mid-Point Assessment

For the mid-point assessment participants will be sent a link to a survey containing the following questionnaires: the Post-Traumatic Stress Scale (Foa et al., 1993), the DASS-21 (Lovibond & Lovibond, 1996), the QLQ-C30 (Aaronson et al., 1993), the PIC (Hulbert-Williams et al., 2019), the UK Cancer Costs Questionnaire, and the CompACT (Francis et al., 2016).

8.7.4. Compliance Assessment

An unblinded member of the research team will check each week for new logins to participants' sixth and final module. Once each participant has commenced their sixth module, this member of the research team will email them a survey containing the Self-Help Compliance Scale (Thiels et al., 2001) to complete.

8.7.5. Post-Treatment Assessment

For the post-treatment assessment participants will be sent a link to a survey containing the following questionnaires: the Post-Traumatic Stress Scale (Foa et al., 1993), the DASS-21 (Lovibond & Lovibond, 1996), the QLQ-C30 (Aaronson et al., 1993), the PIC (Hulbert-Williams et al., 2019), the UK Cancer Costs Questionnaire, and the CompACT (Francis et al., 2016).

8.7.6. 3-Month Follow Up

For the 3-month follow-up assessment participants will be sent a link to a survey containing the following questionnaires: the Post-Traumatic Stress Scale (Foa et al., 1993), the DASS-21 (Lovibond & Lovibond, 1996), the QLQ-C30 (Aaronson et al., 1993), the PIC (Hulbert-Williams et al., 2019), the UK Cancer Costs Questionnaire, and the CompACT (Francis et al., 2016).

8.7.7. 6-Month Follow-Up

For the 6-month follow-up assessment participants will be sent a link to a survey containing the following questionnaires: the Post-Traumatic Stress Scale (Foa et al., 1993), the DASS-21 (Lovibond & Lovibond, 1996), the QLQ-C30 (Aaronson et al., 1993), the PIC (Hulbert-Williams et al., 2019), the UK Cancer Costs Questionnaire, and the CompACT (Francis et al., 2016).

8.7.8. Clinical Data Collection

The following clinical data will be extracted from participants' medical records:

- Date of diagnosis;
- Primary or recurrent cancer;
- Whether the participant was treated with curative or palliative intent;
- The treatment approach adopted for the participant (surgery, chemotherapy, radiotherapy, or watch-and-wait);
- Date of the end of active treatment (if treatment has ended at this point);
- The date of any recurrence or relapse (if applicable);
- Date of death (if applicable);
- Whether the participant received referral to a mental health care professional since their diagnosis of cancer;
- The number of days of inpatient care since study enrolment, and types of healthcare professionals seen during these stays;
- The number of outpatient visits since study enrolment, and types of healthcare professionals seen during these visits; and
- Any diagnosis tests conducted since study enrolment.

8.7.9. Qualitative Interviews

Following participant debriefing for the quantitative component of the clinical trial, we will invite 20-30 trial participants to take part in qualitative interviews assessing the acceptability, and intervention factors affecting the acceptability, of the FMW online programme. Our qualitative interview topic guide is presented in Appendix W.

8.8. Procedures and Assessments

8.8.1. Demographic Characteristics

We will ask participants to self-report the following demographic characteristics: age, gender, sexual identity, employment, education, marital status, and household income.

8.8.2. Post-Traumatic Stress Scale

The Post-Traumatic Stress Scale (Foa et al., 1993) is a 17-item measure of cancer-specific distress. Participants respond on a 4-point Likert scale, where responses are anchored from 0 (Not at all or only one time) to 3 (5 or more times per week / almost always). The Post-Traumatic Stress Scale is associated with excellent internal consistency reliability (α = .91) (Foa et al., 1993). The post-traumatic stress scale has good concurrent validity, including

strong positive correlations with other measures of trauma-related intrusion and avoidance, anxiety, and depression (Foa et al., 1993).

8.8.3. DASS-21

The Depression, Anxiety, and Stress Scales, 21-item version (DASS-21) (Lovibond & Lovibond, 1996) is a short measure of negative emotions experienced over the course of the past week for the individual. Each item is presented as a 4-point Likert scale, anchored as 0 ("Did not apply to me at all"), 1 ("Applied to me some degree, or some of the time"), 2 ("Applied to me to a considerable degree or a good part of the time"), and 3 ("Applied to me very much or most of the time"). The total score for each subscale of the 21-item DASS-21 is calculated by summing participants' responses to the items for each subscale and multiplying this sum by two. Higher scores for each subscale therefore indicate greater levels of depression, anxiety, and stress, respectively. The depression scale of the DASS-21 is associated with excellent internal consistency reliability (α = .91) (Lovibond & Lovibond, 1995). The anxiety scale and the stress scale of the DASS-21 are both associated with good internal consistency reliability (α = .81 and α = .89, respectively) (Lovibond & Lovibond, 1995). The DASS-21 has good concurrent validity, including strong, positive correlations with other measures of depressive symptoms and anxiety (P. F. Lovibond & Lovibond, 1995).

8.8.4. QLQ-C30

The QLQ-C30 (Aaronson et al., 1993) is a 30-item quality of life assessment for cancer patients, which yields a global quality of life score and five functional subscale scores associated with physical, emotional, social, role, and cognitive quality of life domains. The global score for the QLQ-C30 is associated with good internal consistency reliability (α = .86) (Aaronson et al., 1993). The QLQ-C30 is associated with good concurrent validity, with global quality of life and the role functioning and physical functioning scales significantly positively correlated with performance status throughout treatment (Aaronson et al., 1993). The QLQ-C30 score can be converted into an indication of QUALYs to be used in health economic analysis.

8.8.5. The PIC

The PIC (Hulbert-Williams et al., 2019) is a 12-item self-report measure of psychological adjustment to cancer. Each item is presented on a 4-point Likert scale anchored from "Definitely does not apply" to "Definitely does apply". The PIC yields four subscale scores: Cognitive Distress, Cognitive Avoidance, Emotional Distress, and Fighting Spirit. For the purposes of the current study, we will only analyse the Cognitive Distress, Cognitive Avoidance, and Emotional Distress subscales. All subscales are associated with at least fair internal consistency reliability ($\alpha > .623$) and good concurrent validity with longer measures of psychological adjustment to cancer (Hulbert-Williams et al., 2019).

8.8.6. The UK Cancer Costs Questionnaire

The UK Cancer Costs Questionnaire is a modular self-report measure of resource use by people with cancer and people with a previous diagnosis of cancer. The UK Cancer Costs Questionnaire assesses employment status, family support provided, government benefits, and support provided by other organisations over the previous three months. The UK Cancer Costs Questionnaire prioritises brevity in order to minimise the burden of data collection for participants.

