4.4. Secondary Endpoints

Secondary endpoints of the study include depression, anxiety, and stress, as measured by the Depression, Anxiety, and Stress Scales – 21 item version (DASS-21) (Lovibond & Lovibond, 1996); quality of life, as measured by the The European Organisation for Research and Treatment of Cancer Core Quality of Life Questionnaire (version 3.0) (QLQ-C30) (Aaronson et al., 1993); psychological adjustment to cancer, as measured by the Psychological Impact of

Cancer (PIC) Scale (Hulbert-Williams et al., 2019); and health service utilisation, as measured by the UK Cancer Costs Questionnaire.

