module release, the modules will be released in a standard order decided in advance by the research team.

At the beginning of each week, a new cognitive-behavioural therapy-based module will be made available to participants in the active treatment arm, in the order that participants requested. Participants will receive an email reminder about the new available module at this time. Participants in the intervention group will receive an additional text or phone call reminder (depending on their stated communication preference) if they haven't logged in one week after account activation, and an additional phone call reminder if they haven't logged in two weeks after account activation. Module 1 of FMW focuses on orientation to the treatment team, information about complementary therapies, and decision-making. Module 2 focuses on managing physical symptoms and cognitive changes through activity monitoring, relaxation, and meditation. Module 3 focuses on emotion regulation and stress management. Module 4 focuses on issues around cancer and identity. Module 5 focuses on managing relationships with family and friends. Module 6 focuses on transitioning to life after cancer.

Mid-point assessment

At the end of the third week after being informed of their allocation to the waitlist-control or intervention group, the research team will send participants questionnaires assessing cancerspecific distress; anxiety, depression, and general stress; quality of life; psychological adjustment to cancer; health service utilisation; and psychological flexibility. Participants will receive a text or phone call reminder (depending on their stated communication preference) if they have not completed this survey after one week. Participants will receive an additional phone call reminder if they have not completed the survey after two weeks. The research assistant will offer participants the option to complete the survey via telephone at this time, if they prefer. If participants choose to complete the mid-point assessment via telephone, the research assistant will complete the Qualtrics survey for them, according to the participant's telephone responses.

Compliance Assessment

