11.2.4. Health Economic Analyses

The healthcare utilisation outcome will be summarised descriptively for activity counts and cumulative costs. Generalised linear models will be used to adjust for the same confounding variables as the efficacy analysis.

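### A three-month recall asked at weeks 3 and 6 makes the cost questionnaire look back mostly before allocation and recall weeks 0–3 twice, and its described content does not match the utilisation endpoint

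*Protocol*

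**What the plan says.** Section 4.4 lists as a secondary endpoint "health service utilisation, as measured by the UK Cancer Costs Questionnaire". Section 8.8.6 calls the tool a "modular self-report measure of resource use by people with cancer and people with a previous diagnosis of cancer" and gives its content and look-back: "The UK Cancer Costs Questionnaire assesses employment status, family support provided, government benefits, and support provided by other organisations over the previous three months".

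The form is part of the baseline pack (8.7.2) and of all four later packs. Section 8.7.3, for example, ends its mid-point list with "the UK Cancer Costs Questionnaire, and the CompACT". Section 5 sends the mid-point pack "At the end of the third week after being informed of their allocation to the waitlist-control or intervention group" and the post-treatment pack at the end of week 6.

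For the two later visits Section 5 gives two anchors. Its randomisation paragraph schedules all four assessments from the date of being told the allocation. Its follow-up paragraphs count three and six months from receipt of the post-treatment link.

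On analysis, 11.2.4 says: "The healthcare utilisation outcome will be summarised descriptively for activity counts and cumulative costs". Section 8.7.8 separately takes counts from medical records, among them "The number of days of inpatient care since study enrolment", outpatient visits and tests. Nothing shortens the recall at weeks 3 and 6 or says how overlapping answers are combined.

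**The concern.** A three-month look-back asked three or six weeks after allocation mostly describes time that the programme could not have affected. The two early windows also overlap each other and the baseline window. If the answers are added, use before allocation enters the totals and the first weeks of treatment count more than once. If they are analysed as change from baseline, as 11.2.3 plans for each outcome, the week-3 contrast largely compares a period with itself.

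The recall period is fixed when the question is asked. No later analysis can split a three-month total into the part before and the part after allocation.

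The second issue is the source. The endpoint rests on a tool whose described content names no health service, while the hospital counts are collected elsewhere and are not tied to the endpoint.

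**Working it through.** The plan gives no figure to reproduce, so this is interval arithmetic.

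**Inputs.** Recall of three months (8.8.6), taken as 13 weeks (assumption). Visits at weeks 3 and 6 after being told the allocation (Section 5). Later visits at weeks 6 + 13 = 19 and 6 + 26 = 32 on the post-treatment-link anchor, or at weeks 13 and 26 on the allocation-date anchor.

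**Windows.** A form at week t covers t − 13 to t. The part before allocation is max(0, 13 − t).

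| Form | Link anchor | Allocation anchor | Weeks before allocation |
|---|---|---|---|
| Week 3 | −10 to 3 | −10 to 3 | 10 of 13 (77%) |
| Week 6 | −7 to 6 | −7 to 6 | 7 of 13 (54%) |
| 3-month | 6 to 19 | 0 to 13 | 0 |
| 6-month | 19 to 32 | 13 to 26 | 0 |

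**If the four answers are added.** Either way, 4 × 13 = 52 weeks are counted, of which 10 + 7 = 17 precede allocation and 52 − 17 = 35 follow it.
- Link anchor: 32 distinct weeks of follow-up, so 35 − 32 = 3 are duplicated. Ratio 52/32 = 1.63; excess (17 + 3)/52 = 38% of the total.
- Allocation anchor: 26 distinct weeks, so 35 − 26 = 9 are duplicated. Ratio 52/26 = 2.00.
- Leaving out only the week-3 form (link anchor): 39 weeks for 32, ratio 1.22, with 7 still before allocation.

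**Late return.** If every form comes back two weeks late, 8/13 (62%) and 5/13 (38%) of the early windows still precede allocation, and on the link anchor 5 weeks are duplicated.

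**Overlap with baseline.** If baseline is completed at allocation, its window is −13 to 0. It shares 10 weeks with the week-3 form and 7 with the week-6 form. Each week between baseline and allocation takes one week off both overlaps.

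**Effect on estimates.** Assume, for illustration only, constant weekly use and a constant 20% reduction from allocation.
- Relative scale: the apparent reduction is 20% × 3/13 = 4.6% at week 3, 20% × 6/13 = 9.2% at week 6, and 20% × 35/52 = 13.5% in the link-anchor sum.
- Absolute scale: use before allocation cancels between arms in expectation. With a constant weekly difference d, the sum gives 35d where the truth is 32d. That is 35/32 = 1.09, about 9% too large. On the allocation anchor it is 35/26 = 1.35.

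**Content.** 4.4 measures health service utilisation with the questionnaire. 8.8.6 describes employment, family support, benefits and support from other organisations. 8.7.8 collects inpatient days, outpatient visits and tests. Neither 4.4 nor 11.2.4 refers to 8.7.8.

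**The case against.** The strongest reply is that the summing is assumed. Section 11.2.4 speaks of cumulative costs but does not say that the four answers are added or that the questionnaire is the only source. A SAP, not shown here, could set a combining rule. This stands: the 52-for-32 count is conditional. It does not remove the defect, because a combining rule can only discard the early answers. It cannot recover what happened between allocation and week 6 from them.

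Several stronger readings are tempting, and the documents do not support them.
- *Any effect is diluted.* True only on a relative scale. The absolute summed difference is inflated, and 11.2.4 does not state the scale. Constant weekly use is also doubtful in patients diagnosed within the past six months (7.1).
- *The questionnaire asks about no health services.* The instrument is not shown, is called modular, and is a measure of resource use. Only the mismatch between its description and the endpoint is established.
- *The distortion falls exactly where the Australian trial saw its reduction.* Section 2 reports a short-term reduction in service use but names no visit.
- *Hospital records can fill weeks 0–6.* Section 8.7.8 takes totals since enrolment, requested at the 6-month link. They cannot isolate those weeks, and the list does not name GP contacts.

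The records form does offer non-overlapping hospital counts. That is a real mitigation once the endpoint is linked to it.

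**Conclusion.** The point holds for the recall windows and for the source of the endpoint. As the protocol stands, about 77% of the week-3 window and 54% of the week-6 window precede allocation, both overlap baseline, and weeks 0–3 are recalled twice. These shares rest on 13 weeks per three months and on-time return.

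If the post-baseline answers are added unadjusted, absolute use and cost are inflated in both arms (1.63 times the follow-up weeks on the link anchor, 2.00 on the allocation anchor) and noise is added. Early weeks are over-weighted in the between-arm difference. Even without adding, relative effects at weeks 3 and 6 are diluted and the week-3 change from baseline is close to uninformative.

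The choice of anchor changes the size of the overlap, not its existence. The matter touches a named secondary endpoint and the economic summary, not the primary endpoint. It should be corrected.

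**What to change.** 1. **Recall wording, in online, paper and telephone modes.** At week 3 ask about the time since the participant was told their group. At later visits ask about the time since a printed date, namely the previous scheduled assessment. Late returns can still leave a short overlap; a printed end date would close it.
2. **Anchor.** Reconcile the two statements in Section 5 on when the 3- and 6-month assessments fall. The windows then tile the follow-up: 3 + 3 + 13 + 13 = 32 weeks on the link anchor, or 3 + 3 + 7 + 13 = 26 on the allocation anchor.
3. **Answers already collected with three-month recall.** Leave the week-3 and week-6 forms out of cumulative totals, and state that weeks 0–6 then have no separate self-report. On the link anchor those weeks are not covered by self-report at all; on the allocation anchor they are covered only within the 3-month answer.
4. **Source of the endpoint.** In 4.4 and 11.2.4 name the records form as the source of inpatient days, outpatient visits and tests since enrolment. Name the questionnaire as the source of primary care, if its modules cover it, and of other costs. Bring the description in 8.8.6 into line with the instrument.

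The cost is a small amendment, which needs sponsor and REC approval (14.8), and two recall wordings in the data if the change is made mid-trial.
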